Gholizadeh et al. ⁽³⁸⁾ (2017)	Chemotherapy	220 mg capsules equivalent to 50 mg of zinc sulfate 3 times / day 150 mg / day VS. Placebo	Myeloid and lymphoid leukemia 18 - 71 years old	Randomized clinical trial n = 140 4 weeks follow-up (week 2 and 4)	Reduction of severity of OM grade 3-4 p = 0.004
Rambod et al. ⁽¹²⁾ (2018)	Chemotherapy	220 mg capsules equivalent to 50 mg of zinc sulfate 3 times / day 150 mg / day VS. Placebo	Myeloid and lymphoid leukemia > 18 years	Randomized triple blind clinical trial n = 86 14 days WHO oral mucositis scale Oral Mucositis Index	OM prevention p = 0.01 OM severity reduction p = 0.01

OM; Oral Mucositis, HDC: High doses of chemotherapy, HPCT: hematopoietic progenitor cell transplantation.

There are currently no studies evaluating the effectiveness of zinc for the prevention of OM in pediatric patients receiving chemotherapy, so the purpose of this study is to conduct a clinical trial that evaluated the impact of the use of zinc for the prevention of OM in children with LAL in chemotherapy.

PROBLEM STATEMENT

The development of OM in patients with acute leukemia varies between 81.3% and 90% .8 The available literature recognizes the importance of prevention and treatment of OM, since it has an impact on the quality of life and even on the prognosis of disease in patients under chemotherapy. The better understanding of the pathophysiology of this entity has allowed the development of new therapies, among which the use of zinc, which has shown beneficial effects in the prevention of OM in adult patients with leukemia, and because they are not counted with studies in pediatric patients with ALL; The following research question arises:

What is the impact of the use of zinc for the prevention, incidence and reduction of the severity of oropharyngeal mucositis in patients with acute lymphoblastic leukemia in chemotherapy during the period from 2019 to 2020?

JUSTIFICATION

In the National Institute of Pediatrics, about 100 new cases of ALL enter each year, which will require a multidisciplinary approach throughout the course of cancer treatment, which includes the participation of the stomatologist, who must continually establish preventive and therapeutic measures of complications buccal, among which the OM stands out as a reason for frequent consultation.

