Cancer patients will experience pain, limitation and psychological involvement due to oral OM; this debilitating condition also significantly affects nutritional intake, oral care and quality of life, representing up to 21.9% of the reasons for hospitalization.8 OM, if not properly treated or associated with prolonged neutropenia, may end in septic shock and even the death of the patient.

The use of zinc has been studied as a low-cost alternative for OM, so the realization of this study will determine the effectiveness of the use of zinc for the prevention and reduction of complications due to OM in pediatric patients with ALL of the Institute National Pediatrics.

OBJECTIVE

To assess the impact of the use of zinc in the prevention, incidence and severity of oropharyngeal mucositis in patients with acute lymphoblastic leukemia in chemotherapy (induction and consolidation phase) of the National Institute of Pediatrics and the Children's Hospital of Mexico during the period from 2019 to 2020.

SPECIFIC OBJECTIVES

1. Determine the incidence of OM in patients with ALL assigned control group (Group 1: oral care + placebo) versus the intervention group (Group 2: oral care + zinc).
2. Identify if there are differences in OM severity between Group 1 and Group 2.
3. Identify if there are differences in the recovery time of the OM between Group 1 and Group 2.
4. Identify if there is an association between the severity of OM and severe neutropenia in both groups.

HYPOTHESIS

The use of zinc reduces the incidence and severity of OM in pediatric patients with ALL in chemotherapy compared to the control group.

MATERIAL AND METHODS

Type of study: Randomized, double blind clinical trial.

Duration of the intervention: Induction and consolidation phase of chemotherapy (2 to 2.5 months).

Inclusion Period: from August 2019 to May 2020.

Study population

Target population: patients of both sexes from 3 to 18 years of age with newly diagnosed or relapsed ALL during the period from 2019 to 2020.

Study population: patients of both sexes from 3 to 18 years of age with recently diagnosed or relapsed ALL treated by the Pediatric Oncology service of the National Institute of Pediatrics and the Children's Hospital of Mexico during the period from 2019 to 2020.

Selection criteria

Inclusion criteria: Patients aged 3 to 18 years with a recent diagnosis of ALL or relapse who accept by informed consent to participate in the study.

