Exclusion criteria. Patients with another disease or systemic condition in addition to ALL. Presence of oral infections such as candidiasis, herpetic gingivostomatitis, reactive oral lesions. Children with Down syndrome, patients allergic to zinc or mannitol.

Elimination criteria: Patients who present with hypersensitivity to zinc or placebo (mannitol), those who develop a systemic condition that modifies their treatment or prevents oral care, as well as patients requesting to leave the study.

Definition of the variables

INTERVENTION VARIABLE				
	CONCEPTUAL DEFINITION	OPERATIONAL DEFINITION	TYPE	MEASUREMENT
ZINC	Trace element found in most of the body's cells, having catalytic, structural and cellular regulation functions.	Food supplement based on zinc sulfate in doses of 50-100 mg / day for prevention and treatment of oropharyngeal mucositis .	Qualitative Nominal	1. Apply 2. No apply

DEPENDENT VARIABLES				
ORAL HYGIENE	Combination of physical and chemical measures to control the formation of bacterial plaque, which is the most important risk factor in the development and evolution of caries and periodontal disease.	Oral hygiene registered with the O'Leary index (bacterial plaque on dental surfaces identified by a developer. It is obtained from the sum of stained dental surfaces / total surfaces, multiplied by 100.	Qualitative Ordinal	1. Good 0% to 15%: 2. Regulate 16% to 49%: 3. Poor: 3.50% to 100%:
OM RECOVERY DAYS	Days in which some degree of OM is clinically observed until healing.	Number of days from the clinical diagnosis of OM (Grade ≥ 1) to recovery of the oral epithelium.	Continuous	1,2 ,3 4, 5...

INDEPENDENT VARIABLES

ORAL MUCOSITIS	Inflammatory reaction that affects the entire gastrointestinal tract from the mouth to the anus caused by chemo and / or radiotherapy.	Inflammatory reaction of the oropharyngeal mucosa to chemotherapeutic drugs, according to the WHO scale.	Qualitative Ordinal	Grade 0. Healthy Grade 1. Erythema Grade 2. Ulcers Grade 3. Extensive ulcers Grade 4. Ulcers and necrosis.
PAIN	Localized and subjective sensory perception that is the result of an excitation or stimulation of specialized sensory nerve endings.	Visual scale of facial expressions	Qualitative Ordinal	0-2 No pain 3-4 Mild 5-6 Moderate 7-8 Intense 9-10 Maximum

SOCIODEMOGRAPHICAL VARIABLES

	CONCEPTUAL DEFINITION	OPERATIONAL DEFINITION	TYPE	MEASUREMENT

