oropharyngeal mucositis, how it relates to chemotherapy and the preventive measures they can perform. Finally, the complications that may occur during the OM will be explained, such as: difficulty in eating, speaking or swallowing, as well as the measures that must be taken to allow adequate recovery.

Parents will be invited to participate in the protocol explaining the objectives of the study, as well as its risks and benefits. In case of accepting to participate, informed consent and assent (in children over 12 years old) will be presented in accordance with the characteristics that are written in it.

The intervention will be assigned under the balanced block scheme. Children will be randomly assigned to each of the two treatment groups using sealed envelopes.

Oral examination, staining of dentobacterial plaque will be performed (the characteristics of the plaque revealing solution are described in the researcher's manual) for the determination of the oral hygiene index and explanation of brushing technique on day 0 of chemotherapy.

Patients who require dental caries treatment will be rehabilitated by the stomatology service according to their stomatological diagnosis and their general condition. A closed bottle containing 100 tablets (treatment A or B) will be provided according to the random assignment. It will be indicated to administer 1 or 2 tablets daily (according to the age of the patient) from day 1 of chemotherapy.

A written reminder will be provided to parents in which they must check each day if the tablet was taken.

Calls will be made every 3 days to verify that oral hygiene and tablet administration are being carried out; In addition, the reminder will be reviewed twice a week and the remaining tablets will be counted in the bottles.

During the course of chemotherapy (induction and consolidation phase) reviews will be performed on days 1, 4, 7, 14 and 21 of each cycle.

Maneuver

Group 1 (oral care + placebo): gentle tooth brushing with a soft bristle brush 3 times a day and mouthwash with baking soda after each meal (1/4 tablespoon of baking soda dissolved in water to make a mouthwash for 3 minutes) plus the consumption of 1 or 2 oral placebo tablets (mannitol) from day 1 of chemotherapy.

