Six randomized patients with a recent diagnosis of childhood cancer who start chemotherapy will be selected, data from the clinical record will be obtained to determine if it meets the inclusion criteria. The patient identified as eligible will be visited at his place of hospitalization or in the outpatient office of the Oncology Service.

The intervention will be assigned under the balanced block scheme. Children will be randomly assigned to each of the two treatment groups using sealed envelopes.

The sequence of procedures and the complete description of the instruments can be found in the Annex "Pilot test applicator manual".

[figure not shown]
Information collection method

A data record sheet will be filled out that includes the patient's identification form (name, age, sex), type of ALL, chemotherapy phase and blood count; which will be obtained from the clinical file. It will also include the table for the determination of the WHO OM scale, the oral hygiene index and the opportunistic infection registry.

Registration and processing method.

[figure not shown]
The data will be recorded in an Epidata database and analyzed using the STATA 14 statistical program.

FLOWCHART 1

In the previous study by Rambod et al. (12), a difference in the incidence of OM of 28% was obtained and from this, for the present study the estimated sample size was 106 subjects.

Complying with one of the principles that govern clinical trials, which is to reduce the risk of the operated subjects to the minimum possible, in case of observing adverse reactions the suspension of the study will be indicated; while if there are no complications, recruitment will continue until a sample size of 53 subjects is met and at this point the intermediate analysis will be performed as shown in Flowchart 2.

ETHICAL CONSIDERATIONS

In accordance with the principles and guidelines established by good clinical practices (BPC), in accordance with the principles set forth in the Helsinki Declaration of 1964 and with the support provided in the General Health Law, in the Regulations of the General Health Law in the area of provision of Health Care Services, which establishes that the individual welfare of the subjects must sometimes prevail in a study, over the interests of science and the community.

This study will be carried out with the strict observation of the recognized scientific principles and respect, handling the affected data anonymously and confidentially.

Consent

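### Suspension of the study depends on adverse reactions, but no adverse-reaction item appears among the listed variables, data-sheet contents, telephone checks or planned analyses

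*Combined protocol and SAP*

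**What the plan says.** - **Suspension and the look (text under Flowchart 1).** The planned total is 106. The rule is that "in case of observing adverse reactions the suspension of the study will be indicated". Without complications, recruitment goes on "until a sample size of 53 subjects is met and at this point the intermediate analysis will be performed as shown in Flowchart 2".
- **Risk (Ethical Considerations).** The study is rated above minimum risk. The same paragraph calls 50-100 mg/day safe because no adverse effects are described at that dose.
- **Known reactions (Secondary and adverse reactions, and the paragraphs after it).** Nausea, vomiting, diarrhoea, abdominal pain and allergic signs are listed. Nausea is put at 20% under gastrointestinal toxicity, which is described as apparently dose related. Anaemia and leukopenia are also named.
- **Data sheet (Information collection method).** It holds identification, type of ALL, chemotherapy phase and blood count. "It will also include the table for the determination of the WHO OM scale, the oral hygiene index and the opportunistic infection registry".
- **Contacts (Stages of the study and data collection).** Reviews fall on days 1, 4, 7, 14 and 21 of each cycle. "Calls will be made every 3 days to verify that oral hygiene and tablet administration are being carried out".
- **Single children (Elimination criteria).** A child with hypersensitivity to zinc or mannitol leaves the study.
- **Manual (Toxicity management).** How the researchers respond to reactions is left to the investigator's manual, which is not among the documents.
- **Statistical Analysis Plan.** It names descriptive statistics, t-test, chi-square and ANOVA, with no safety summary.

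**The concern.** A stopping condition works only if the event it names is recorded in the same way for every child. Here the event is an adverse reaction, and the places where one would expect it to be defined, asked about, written down and tabulated do not mention it. If reactions reach the investigators only when a parent happens to report one, the absence of complications at 53 children could mean that there were none or that nobody asked. Analysts cannot recover these data later.

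The stakes are more than formal. The protocol describes itself as the first trial of zinc for preventing mucositis in children and says that earlier studies give no reference dose (Zinc dose determination). Tolerability at 50-100 mg/day in this population is therefore something that the trial should be able to report by group.

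The wording adds a second problem. The rule gives no severity and no relation to the tablets, so any reaction in either group meets it as written.

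**Working it through.** **1. The plan's own numbers.** Sample size calculation: 46 per group, 46 × 1.15 = 52.9, so 53 per group and 106 in total. The look at 53 is 53/106 = 50% of planned recruitment. With 1:1 allocation in blocks of 6, that is about 26 zinc children.

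**2. Where an adverse reaction would have to appear.**

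| Place | Contents | Gastrointestinal or allergic reaction listed? |
|---|---|---|
| Definition of the variables | Zinc, hygiene, recovery days, mucositis, pain, age, sex, ALL type, neutropenia, infections | No |
| Data sheet | Identification, ALL type, phase, blood count, mucositis scale, hygiene, infections | No |
| 3-day calls | Hygiene and tablet-taking | No |
| Statistical Analysis Plan | Descriptive statistics, t-test, chi-square, ANOVA | No |
| Elimination criteria | Hypersensitivity removes the child | Allergic only, as a reason to leave |
| Toxicity management | Refers to the manual | Response only |

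Blood count and neutropenia give partial cover for haematological effects. Nausea, vomiting, diarrhoea and abdominal pain have no listed place.

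**3. What no reactions at the look would show.** With complete recording, zero events in n children exclude rates above 1 − 0.05^(1/n) (one-sided 95%).

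- n = 26: 1 − 0.05^(1/26) = 10.9%.
- n = 53 (the full zinc group): 1 − 0.05^(1/53) = 5.5%.

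If only a share s of reactions is captured, the limit for the true rate is the same figure divided by s. The documents give no s. As assumptions, s = 0.75 gives 10.88/0.75 = 14.5%, s = 0.5 gives 21.8%, and s = 0.25 gives 43.5%. Without a uniform question, s is unknown and may differ between children.

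**4. How easily the literal rule is met.** The chance of at least one reaction in 26 zinc children is 1 − (1 − p)^26. The documents give 20% for nausea without a dose, so p is varied as an assumption.

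- p = 1%: 23.0%
- p = 5%: 73.6%
- p = 10%: 93.5%
- p = 20%: 99.7%

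Nausea or vomiting caused by chemotherapy, in either group, would raise these figures, because the rule does not ask about cause.

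**The case against.** **The list may not be complete.** The data sheet is said to include its items. Pain and recovery days are defined variables, yet they are missing from that list too, so it is not exhaustive. Figures beside the text are not shown, and the manual may hold a reaction form. This stands, and it rules out the stronger reading that reactions will go unrecorded. It does not explain why the variable tables and the analysis plan are also silent, or why the manual is cited only for the response.

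**Staff will see the children often.** The five visits per cycle and the 3-day calls are real chances to notice a reaction, and the elimination criterion presumes that hypersensitivity is noticed. Noticing is not a uniform record, but the contacts make the remedy cheap.

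**The two rules do not conflict.** Removing one child and suspending a study are different levels of action, and the manual may give severity and causality. A reader might infer a contradiction; there is none, only a study-level rule whose readable wording has no threshold.

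**The look itself.** A reader might infer that the plan has an interim analysis without endpoint or decision, and that its type I error is inflated. The documents do not support this. The look is carried out as Flowchart 2 shows, and that figure was not extracted. Under the null hypothesis, testing at two-sided 0.05 at both the look and the end gives an overall error of 8.3% at half the information and 9.1% at a quarter. That applies only if an efficacy claim is allowed both times. A safety-only look changes nothing, and a no-difference stop does not raise the error. The Benefits paragraph, garbled as it is, hints at suspension when no difference is found, but does not tie it to the look.

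**Timing.** A reader might also object that the look follows recruitment, so many children are still on treatment. Under even accrual of 106 in 10 months, or an assumed 100 per year, those children average half a course. The 53 then hold 75-84% of their planned treatment time. At 10.6 per month with 2.5 months of treatment, for example, (53 − 26.5/2)/53 = 75%. About 46-47 would have a full first 21-day cycle. This is not a defect worth pressing.

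**Conclusion.** The point holds as a gap in recording and analysis. Suspension of a trial rated above minimum risk depends on an event that the readable variables, data-sheet list, calls and analysis plan do not contain. For gastrointestinal and allergic reactions, neither the suspension condition nor a comparison between groups could be checked from the listed data.

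The size depends on capture: a zero-event limit of 10.9% in 26 zinc children with full recording, and 14.5-43.5% if between three quarters and one quarter of reactions are captured. Read literally, the rule would more likely than not be met by the look if 5% or more of zinc children had any reaction.

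This rests on the readable text. A form in the manual or in a figure could close part of the gap, so confidence is moderate. The endpoint, decision and any alpha for the look at 53 remain a query.

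**What to change.** 1. **Record.** Add adverse reactions (type, grade, date, related to the tablets or not) to the variable tables and the data sheet. Ask about them at the existing visits on days 1, 4, 7, 14 and 21 and at the 3-day calls.
2. **Analyse.** Add one line to the Statistical Analysis Plan: number and proportion of children with each reaction, by group, at the end of the study.
3. **Reword the suspension rule.** Limit study-level suspension to serious reactions judged related to the tablets. State that removing one child under the Elimination criteria does not suspend the study. Bring in any criteria that the manual already holds.
4. **Protect the blind.** Any summary by code A or B before the end should go only to the independent investigator who holds the code. With two codes for the whole trial, an imbalance in reactions seen by the examiners could reveal the treatment of every child.
5. **Ask the sponsor** what Flowchart 2 decides at 53 recruited: the endpoint, the decision, any alpha, and whether it is the no-difference suspension hinted at under Benefits.

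The cost is one more question and one more field at each contact, plus a few sentences of text. Steps 1 to 4 use no alpha or power and need no extra children or delay.
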